5.1.2 Phase 2 dose expansion cohort

Once the RP2D is determined, an additional cohort of patients with r/r PTCL will be enrolled to further assess the efficacy and tolerability of AZD4205. Approximately 100 patients with r/r PTCL are planned to be enrolled, while as the result of this part is planned to support an NDA submission for AZD4205, the sample size will be discussed and agreed with regulatory authorities before initiation of enrollment. Patients will receive AZD4205 treatment until disease progression, unacceptable toxicity, discontinuation criteria have met, withdrawal of consent or termination of the study by Sponsor.

Stopping criteria for dose expansion cohort (Part B)

In Phase 2 dose expansion cohort (Part B), around 100 patients with r/r PTCL are planned to be enrolled continuously and receive AZD4205 at 150 mg once daily. TEAE related discontinuation or death will be continuously monitored. After \geq 20 patients are enrolled and once the rate of TEAE related discontinuation or death reaches \geq 19.7%, an ad-hoc SRC meeting will be triggered to review all available safety, tolerability and efficacy data of Part B. In the case of treatment-related death occurred (\geq 1), the study accrual will be suspended and SRC meeting will be triggered. The decision of SRC may be to:

- Make decisions on the patient recruitment plan, e.g. enrollment suspension and resumption.
- Adjust the risk management plan for the expansion cohort (Part B)
- Re-evaluate the risk-benefit balance

The criteria of 19.7% is calculated based an algorithm close to Bayesian Optimal Interval (BOIN) design (Liu S et al. 2015). We will set our target rate as 15% and un-acceptable rate as 25%. The boundary is calculated similar to λ_d in BOIN design. The un-acceptable rate of 25% is set based on TEAE leading to dose discontinuation rate in pivotal trials of approved drugs for r/r PTCL, which ranges from 19 to 23% (Coiffier B et al, 2012; O'Connor OA et al. 2011; O'Connor OA et al, 2015). While target rate is similar to our current observed TEAE leading to dose discontinuation rate of 13.9% (Data from Part A of DZ2019J0005 study as of September 11, 2020).

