	QT prolongation (QTcF > 450 ms) with signs/symptoms of life-threatening arrhythmia	Permanent discontinuation
	Confirmed drug-induced pneumonitis (any grade, see Figure 3)	Permanent discontinuation
	Grade 4 non-hematological toxicity	Permanent discontinuation
		Immediate interruption of AZD4205
Non-		Once toxicity has resolved to recovery to \leq Grade 2 or baseline within 21 days of onset:
hematological	Grade 3 Herpes Zoster	 Resume at the same dose for the 1st occurrence of the event
toxicity		 Resume at the reduced dose for the 2nd occurrence of the event
		 Permanent discontinue for the 3rd occurrence of the event
		Immediate interruption of AZD4205
		Once toxicity has resolved to recovery to \leq Grade 2 or baseline within 14 days of onset:
	Other Grade 3 or unmanageable non-hematological toxicity(ies)	Resume at the reduced dose for the 1st occurrence of the event, unless the toxicity can be safely and reliably controlled to \(\leq \text{Grade 2} \) or baseline
		with appropriate treatment, (toose may restait at 150 mg once daily after reaching an agreement with the sponsor).
		■ If the same non-hematological toxicity requiring dose interruption occurs again, AZD4205 should be permanently discontinued.

The reduced dose level of AZD4205 refers to 75 mg once daily. Patient should discontinue the study treatment, if he/she is already at the reduced dose level (75 mg) and requiring a further dose reduction due to toxicity according to the modification plan (as defined in Table 1).

If medically appropriate, Grade 4 abnormalities of hematology parameters which are considered to be of clinical concern may be repeated/confirmed within 7 days and followed up as appropriate. Supportive care such as transfusion and/or growth factor could be given per institutional guideline.

Supportive care for the management of the toxicities may be given to the patients as required in accordance with local practice/guidelines. Patients should permanently discontinue the study treatment, if the toxicities leading to interruption do not recover to ≤ Grade 2 or baseline within the maximum duration of dose interruption defined in Table 1. Patients with toxicities leading to dose discontinuation should be followed up until Grade 1 or baseline. Deviations from above guidelines may occur based on the clinical judgment of the Investigator with reaching agreement with the Medical Monitor/Sponsor.

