5.2.3 Overall benefit-risk and ethical assessment

For PTCL patients who have progressed on or are refractory/intolerant to standard treatment, the prognosis is very poor as there is no effective treatment available. This study aims to evaluate a JAK1 inhibitor, AZD4205, which potentially provides benefit to this

population with high unmet medical need, as JAK/STAT pathway has been documented to be associated with disease biology. In addition, the selectivity profile of AZD4205 against other JAK family members might provide a better tolerability profiles in clinic. Moreover, the longer half-life of AZD4205, compared with other JAK inhibitors, could potentially achieve longer duration of inhibition of JAK/STAT pathway, and thus drives better clinical activity.

The starting dose of AZD4205 is selected based on non-clinical toxicity findings as well as clinical data derived from the completed study of AZD4205 in EGFRm advanced NSCLC in Australia. The selected doses of 150 mg and 250 mg once daily are predicted to achieve biologically effective exposure and thus potentially derive clinical benefit to patients with PTCL.

Preliminary safety data at 150 mg and 250 mg suggests AZD4205 was tolerated at both doses. The most common \geq grade 3 drug related TEAEs (defined as incidence rate \geq 5%) included thrombocytopenia, neutropenia and pneumonia. The majority of TEAEs were manageable and reversible. These findings were consistent with the predicted safety risks of AZD4205. The current safety monitoring and management plan in Part A could identify these safety risks, and thus will be applied in the pivotal study (Part B).

Therefore, the benefit/risk assessment for this phase I/II study appears to be acceptable.

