6.5.3 Recording of adverse events

Time period for collection of adverse events

AEs will be collected and recorded in eCRF from first dosing of AZD4205 until the end of the follow up period. The follow-up period is defined as 28 days (± 7 days) after study treatment is discontinued. However, SAE should be collected and recorded in eCRF from ICF signing to the end of defined follow-up period (see Table 5).

Table 5 Summary of recording and follow-up of adverse events

	Consent to Randomization/first dosing	Until defined Follow up Visit (safety follow-up period)	Post Follow-up visit but prior to progression (if applicable)
Record all new AEs in CRF	No*	Yes	No
Record all ongoing AEs in CRF	No	Yes	No**
Record all study procedure related new SAEs in CRF	Yes	Yes	No***

^{*} Adverse events prior to the first dosing but worsening post the first doing should be recorded in eCRF as new AEs.

** All ongoing AEs/SAEs post safety follow-up period will be followed by investigator as long as medically indicated, but without further collection in eCRF.

After the final database lock, there may be some patients remaining on study treatment. For these patients who are continuing to receive AZD4205, Sponsor will collect information (during the treatment period and for 28 +/- 7 days after last dose) on SAEs, deaths (including those due to disease progression), discontinuation due to AEs/SAEs and drug accountability only.

^{***} New emerging SAEs post follow-up period including death should not be collected in eCRF, but still need to be reported to Dizal in the condition of causality with study procedure judged by investigator.

Follow-up of unresolved adverse events

Sponsor retains the right to request additional information for any patient with ongoing AE(s) at the end of the study, if judged necessary.

If an investigator learns of any SAEs, including death, at any time after a patient has completed the study and he/she considers there is a reasonable possibility that the event is related to AZD4205, the investigator should notify Sponsor.

Variables

The following variables will be collected for each AE:

- AE diagnosis/description
- The date when the AE started, stopped and intensity changed
- CTCAE grade (version 5.0); for the grading of specific ocular AEs, refer to Appendix VII (Table 18)
- Whether the AE is serious or not
- Investigator causality rating against the investigational product (yes or no)
- Action taken with regard to investigational product
- Outcome

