6.5.4 Reporting of serious adverse events

All SAEs have to be reported, whether or not considered causally related to the investigational product, or to the study procedure(s). SAEs should be reported to Dizal and recorded in CRF according to Section 6.5.3.

If any SAE occurs in the course of the study, then investigators or other site personnel inform appropriate Sponsor representatives immediately, or **no later than 24 hours** of when he or she becomes aware of it.

The designated Sponsor representative works with the investigator to ensure that all the necessary information is provided to appropriate patient safety database within one calendar day of initial receipt for fatal and life-threatening events and within five calendar days of initial receipt for all other SAEs.

For fatal or life-threatening adverse events where important or relevant information is missing, active follow-up is undertaken immediately. Investigators or other site personnel inform Sponsor representatives of any follow-up information on a previously reported SAE immediately, or no later than 24 hours of when he or she becomes aware of it. The SAE will be reported to the designated sponsor representative via the study SAE paper form.

The Sponsor representative will advise the investigator/study site personnel how to proceed.

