6.9.5.1 Progression free survival follow-up

Patients' tumor response should be followed according to the study plan (Table 2 and Table 3) till confirmed disease progression per Lugano criteria, death or withdrawal of consent. Under circumstances of dose discontinuation for reasons other than progression, response assessments should be continued per study plan until confirmed disease progression.

Beyond the 28-day follow up visit only subsequent cancer therapy and response assessment (if applicable) should be collected.

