- C. In the Phase 2 expansion, following disease progression, the patient, patient's family, or the patient's current physician must be contacted every 3 months for survival information, for collection of details of subsequent treatment regimens received following withdrawal from study drug and to follow up unresolved AEs (unless the patient withdraws consent) regardless of date of last contact.
- D. Both HBsAg and HBcAb should be negative for eligibility.
- E. PFTs (including spirometry and DLCO) will be performed at screening, Cycle 3 Day 1 and then every 6 weeks and whenever clinically indicated.
- F. AEs will be collected and recorded in CRF from first dosing of AZD4205 until the end of the follow up period (28 ± 7 days post last dose). However, SAE should be recorded in CRF from ICF signing to the end of defined follow-up period.
- G. Echoangiogram or MUGA scan to assess LVEF will be conducted at screening (prior to first dose of AZD4205), Cycle 3 Day 1, then every 12 weeks for the rest of cycle.
- H. In the Phase 2 expansion, laboratory tests for screening should be performed within 7 days prior to the planned first dosing date. In addition, laboratory tests do not need to be repeated at baseline if the baseline visit is within 3 days of the screening sample.
- I. In the Phase 2 expansion, submission of the tumor block or unstained slides from a diagnostic biopsy is required for retrospective central confirmation of disease histologic subtype. The diagnostic specimen needs to be from a malignant lymph node or extra-nodal tissue obtained by excisional biopsy.
- J. Patients at the selected sites will be invited for intense PK study on Cycle 1 Day 1 and Cycle 2 Day 1.
- K. Blood sampling for pSATA₅ inhibition of blood cells is only mandatory for patients enrolled in the designated sites.
- L. Blood sampling for pharmacogenetics research at screening is optional for patients enrolled in the Part B.
- M. Pre-treatment tumor assessment should be performed within 28 days prior to (preferably close to) the first dose, including a computed tomography (CT) scan (with contrast unless contraindicated) of the neck, chest, abdomen, and pelvis and any other disease sites (e.g., neck). During treatment, CT scans will be done for tumor assessments within 7 days of Day 1 of Cycle 3, 6, 9 and then every 3 cycles thereafter until PD.

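### Closing the eCRF on adverse events still ongoing at the 28-day contact can leave a later fatal outcome out of the SAP's fatal-TEAE rows

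*Protocol*

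**What the plan says.** Protocol 6.5.3 collects AEs in the eCRF from first dose, and SAEs from consent, to the end of a follow-up period of 28 (±7) days after treatment stops. Grade, outcome, and the dates of start, stop and change in intensity are collected for each AE. Table 5 has a row for AEs already on record and still ongoing. Its last column, headed as the time after the follow-up visit and before progression, answers No for that row, with the double-asterisk footnote: "All ongoing AEs/SAEs post safety follow-up period will be followed by investigator as long as medically indicated, but without further collection in eCRF". SAEs that first arise after the follow-up period have their own footnote and are not the subject here.

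Other provisions on the same point:

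- Protocol 6.5.4, on SAE reporting: "SAEs should be reported to Dizal and recorded in CRF according to Section 6.5.3".
- Protocol 6.9.5.1: "Beyond the 28-day follow up visit only subsequent cancer therapy and response assessment (if applicable) should be collected".
- Protocol Table 3 footnote C, repeated in SAP Appendix A, gives the 3-monthly contact after progression a further task: "to follow up unresolved AEs (unless the patient withdraws consent) regardless of date of last contact". It does not say where the result is recorded.
- Protocol 5.1.3.1: "Patients with toxicities leading to dose discontinuation should be followed up until Grade 1 or baseline".
- SAP 4.3.2 works from AEs recorded on the CRF. A TEAE is an event whose start or worsening falls between first dose and 28 days after last dose, or the day before new anti-cancer therapy if earlier.
- SAP 5.7.1 counts fatal TEAEs and drug-related fatal TEAEs in the overview table and by system organ class and preferred term. Separately, it counts deaths up to 28 days and more than 28 days after last dose, with reasons, and lists all deaths.

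**The concern.** The SAP decides whether an event is a TEAE from when it began or worsened, and sets no limit on when its outcome becomes known. The protocol stops recording the outcome at the 28-day contact. An event can thus qualify as a TEAE while the field that would mark it fatal is closed.

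This affects the fatal and drug-related fatal TEAE rows of Part B, which the protocol intends for a marketing application. The error can only lower these rows. Serious lung infection is a credible route: Protocol 5.2.3 reports that the most common drug-related TEAEs of grade 3 or higher (incidence at least 5%) "included thrombocytopenia, neutropenia and pneumonia". The plan also expects AEs to be ongoing at the contact, since Table 5 has a row for them.

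**Working it through.** The plan gives no figure on this point to reproduce. The check is a trace through the text, then a calculation of scale.

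**Trace.** Take a patient who stops AZD4205 for an AE, without progression, and later dies of that AE.

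1. Onset is on treatment or within 28 days of last dose, so the event is a TEAE (SAP 4.3.2).
2. At the 28 (±7)-day contact it is ongoing. The eCRF holds a non-fatal outcome and the grade reached so far.
3. The Table 5 footnote ends eCRF collection for this event. The patient has not progressed, so the column heading applies as well.
4. The patient dies of the event. Section 6.5.4 calls for SAE follow-up information to go to the sponsor on a paper form, but for CRF recording it points back to 6.5.3, where collection has ended.
5. SAP 5.7.1 builds the fatal rows from the CRF record. As recorded, the event is a non-fatal TEAE. It is absent from both fatal rows and sits at too low a grade in the maximum-grade tables.
6. SAP 5.7.1 still counts the patient among deaths more than 28 days after last dose (or up to 28 days, if the contact was early), with the reason, and lists the death.

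The death could not be set aside as a separate late event. Section 6.5.3 records changes in intensity within an AE, which points to one record governed by its onset.

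After progression the trace is less certain at step 3. The column heading no longer covers the patient, although the footnote has no such limit. Footnote C has unresolved AEs followed up but does not mention the eCRF.

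**Scale.** Input: n = 100, the planned Part B enrolment (Protocol 7.2), taken as the number treated.

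- Shift per missed event: 1/100 = 1.0 percentage point.
- Exact (Clopper-Pearson) 95% limits for 0/100: lower 0; upper 1 − 0.025^(1/100) = 3.6%.
- For 1/100: lower 1 − 0.975^(1/100) = 0.03%; upper, the 97.5% point of Beta(2, 99), = 5.4%.

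| True count | Exact 95% CI | Count if one is missed | Exact 95% CI |
|---|---|---|---|
| 1/100 | 0.03% to 5.4% | 0/100 | 0% to 3.6% |
| 4/100 | 1.1% to 9.9% | 3/100 | 0.6% to 8.5% |

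The counts are illustrative assumptions. The documents give no rate of late fatal outcomes.

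**The case against.** The strongest reply is that the death is reported and counted elsewhere. Protocol 6.5.3 (handling of deaths) covers deaths during the study and requires the causal AE to be reported as an SAE within 24 hours unless death is clearly due to progression. Section 6.5.4 requires follow-up information on a reported SAE within 24 hours and sets no end date. Section 6.5.3 also asks investigators to notify the sponsor of any SAE, including death, that they consider possibly drug-related, even after the patient has completed the study. SAP 5.7.1 summarises late deaths with reasons. All of this stands, and it narrows the point to the AE record. None of it puts the fatal outcome into the record behind the fatal rows, and the death summary is not specified by drug-relatedness or by preferred term.

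Three further replies carry weight. Section 6.9.5.1 cannot be a complete collection rule, because survival data are also collected after the 28-day visit, so it supports the footnote only weakly. CRF completion guidance or data-management documents, which are not available here, may require SAE outcomes to be reconciled into the AE data; the protocol and SAP are silent on this. The SAP was written on protocol version 5.0, whereas the footnote is read from version 6.0.

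A reader might infer more than the text allows. One inference is that such deaths are hidden from the sponsor or that the accrual-suspension rule in Protocol 5.1.2 fails; the reporting provisions above do not support that. Another is that the 13.9% Part A rate of discontinuation for TEAEs measures how many patients are affected. It does not: it says nothing about how many events are ongoing at the contact and later fatal, and patients who stop for other reasons can also have ongoing AEs.

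**Conclusion.** The concern holds in a narrow form. Followed as written, the footnote lets a TEAE that begins in the window and later proves fatal keep a non-fatal outcome and grade, so the fatal and drug-related fatal TEAE rows can be too low. This is clearest for patients who stopped without progression and ambiguous after progression. What can be lost is the link from the death to the TEAE and its drug-relatedness, not the death or its reason.

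The size is 1 percentage point per missed event at n = 100. The number of such events is unknown and probably low. At the lower extreme, one missed event turns one drug-related death into none.

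The conclusion assumes that sites follow the footnote literally and that no unseen document has SAE outcomes reconciled into the analysis data. The primary endpoint, SAE reporting to the sponsor and the accrual-suspension rule are not shown to be affected. This is a cheap improvement of low-to-moderate priority.

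**What to change.** **Protocol.** Amend the double-asterisk footnote to Table 5 and align 6.9.5.1. For SAEs and drug-related AEs ongoing at the 28-day contact, update in the eCRF the outcome, the end date and, if fatal, CTCAE Grade 5 and the date of death. Do this at the existing response assessments (every 3 cycles, 3 × 21 = 63 days) and 3-monthly survival contacts, until resolution, stabilisation, death or data cut-off. The grade must move with the outcome; otherwise the maximum-grade tables would contradict the fatal rows.

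**SAP 5.7.1.** State that a TEAE with onset in the window counts as fatal if the investigator records it as the cause of death by data cut-off, and flag deaths after new anti-cancer therapy.

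**Cost.** Wording changes in two places in the protocol and one sentence in the SAP. No new visits are needed, and 5.1.3.1 already requires toxicities that led to discontinuation to be followed to Grade 1 or baseline. The downside is modest extra data entry and cleaning, and possibly slightly higher fatal-TEAE counts.

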6.5.4 Reporting of serious adverse events

All SAEs have to be reported, whether or not considered causally related to the investigational product, or to the study procedure(s). SAEs should be reported to Dizal and recorded in CRF according to Section 6.5.3.

If any SAE occurs in the course of the study, then investigators or other site personnel inform appropriate Sponsor representatives immediately, or **no later than 24 hours** of when he or she becomes aware of it.

The designated Sponsor representative works with the investigator to ensure that all the necessary information is provided to appropriate patient safety database within one calendar day of initial receipt for fatal and life-threatening events and within five calendar days of initial receipt for all other SAEs.

For fatal or life-threatening adverse events where important or relevant information is missing, active follow-up is undertaken immediately. Investigators or other site personnel inform Sponsor representatives of any follow-up information on a previously reported SAE immediately, or no later than 24 hours of when he or she becomes aware of it. The SAE will be reported to the designated sponsor representative via the study SAE paper form.

The Sponsor representative will advise the investigator/study site personnel how to proceed.

6.6 Pharmacokinetics

6.6.1 Collection of PK samples

6.6.1.1 Part A Dose escalation and extension cohorts

Samples to evaluate the PK of AZD4205 will be taken. Estimated sampling time points are shown here. Discussions will be required with the Dizal PK representative as to any effect on the PK sample schedule if dose interruption occurs within 3 days of PK sampling. The date and time of collection of each sample and the date and time of dose will be recorded. The timing of the PK samples may be adjusted during the study, dependent on emerging data, in order to ensure appropriate characterization of the plasma concentration-time profiles. Updated timings will be provided outside of the protocol and will be documented.

A 5 min window will be allowed for samples taken at 0.5 h and 1 h; a 10 min window for samples taken at 1.5 - 10 h; a 15 min window for samples taken at pre-dose; a 1 h window for samples taken at 24 h.

Samples will be collected, labelled, stored and shipped as detailed in the Laboratory Manual.

Cycle 1 (multiple once daily dosing):

Day 1 (PK profile on day 1 within 24 hr): Pre-dose and at 0.5, 1, 1.5, 2, 2.5, 3, 4, 6, 8, 10 and 24 hours post-dose (**prior to next dose**).

Day 8 and 15: Trough blood sample (pre-dose, 2 mL). Plasma samples (~ 1 mL) will be used for quantification of AZD4205.

Collect PK blood samples (approximately 2 mL each time point) using 2 mL lavender top (EDTA) Vacutainer® evacuated collection tubes at the time points indicated. The date and time of collection of each sample will be recorded. Plasma samples (~1 mL) will be used for quantification of AZD4205.

Cycle 2 (multiple once daily dosing):

Day 1 (PK profile at steady state): Pre-dose and at 0.5, 1, 1.5, 2, 2.5, 3, 4, 6, 8, 10 and 24 hours post-dose (prior to next dose).

Collect PK blood samples (approximately 2 mL each time point) using 2 mL lavender top (EDTA) Vacutainer® evacuated collection tubes at the time points indicated. The date and time of collection of each sample will be recorded. Plasma samples (~1 mL) will be used for quantification of AZD4205.

Cycle 3 and 4 (multiple once daily dosing):

Day 1: Trough sample (pre-dose, 2 mL) Plasma samples (~1 mL) will be used for quantification of AZD4205.

Collect PK blood samples (approximately 2 mL each time point) using 2 mL lavender top (EDTA) Vacutainer® evacuated collection tubes at the time points indicated in Table 6. The date and time of collection of each sample will be recorded. Plasma samples (~1 mL) will be used for quantification of AZD4205.

Table 6 PK blood sampling schedule (Part A)

Time relative	Cycle	1 (multip	le dose)	Cycle 2 (multiple dose)	Cycle 3 (multiple dose)	Cycle 4 (multiple dose)
to dose	Day 1	Day 8	Day 15	Day 1	Day 1	Day 1
Pre-dose	×	×	×	×	×	×
0.5 hours	×			×		
1 hour	×			×		
1.5 hours	×			×		
2 hours	×			×		
2.5 hours	×			×		
3 hours	×	1		×		
4 hours	×			×		
6 hours	×			×		
8 hours	×			×		
10 hours	×			×		
24 hours	×			×		

Footnote: The PK sampling at 24 hours post dosing should be taken before the next dose.

